#### Hypothesis:

- Pembrolizumab is much better tolerated than conventional chemotherapy in CUP patients and PS2 patients may also benefit.

### 2.3 Exploratory Objective

#### Objective:

- Identification of genomic biomarkers predictive of immune response to Pembrolizumab.

#### Hypotheses:

- CUP patients have identifiable biomarkers predictive for Pembrolizumab efficacy.
- CUP patients have high mutational loads and this correlates with increased efficacy with Pembrolizumab.

CUPem	C/37/2017	Imperial College London	V7.0; 08.12.2021
-------	-----------	----------------------------	------------------

### 3 STUDY DESIGN

#### 3.1 Overall Study Design

An open label, non-randomised, single arm, sequential phase (two sequential cohorts) study, evaluating the preliminary efficacy of Pembrolizumab in Cancer of unknown Primary (CUP).

A substantial amendment in February 2022 has formally closed the second cohort, due to the significant challenges in recruitment caused by the ongoing COVID-19 pandemic as well as associated clinical factors.

##### **Cohort 1:**

Cohort 1 will enrol a minimum of 31 patients and a maximum of 67 patients, who have had at least one prior line / regimen of chemotherapy (at least 2 cycles) appropriate for CUP and who have not had a RECIST response to first-line chemotherapy, or are progressing after an initial response, or are treatment intolerant to first-line chemotherapy, due to unacceptable toxicity.

##### **Cohort 2:**

Cohort 2 is now formally closed. This cohort had sought to enrol patients who are chemo-naïve (first-line setting) for CUP, with a PS 0-2.

\*\*\*\*\*

Patients will undergo screening procedures during a standard 28-days time window from initiation of the study, under standard GCP and informed consent. Restaging will be performed by computerized tomography using ir-RECIST criteria at 3 months from initiation of systemic treatment and on an 8 weekly basis thereafter until radiological proven disease progression or intolerance or patient choice.

The EORTC QLQ-C30 questionnaire (to assess the quality of life) will be done at baseline after 3 months and then at discontinuation of study treatment.

Correlative translational study samples (blood) and tissue (used for histological confirmation and to document PD-L1 expression) will be collected at baseline, and blood and serum samples monthly (after an informed optional consent and banked for retrospective immune-modulating and other biomarkers for future research and analysis). Patients will also be separately consented to the NHSE CUP 100K genome project that will be running in the UK by 2018, for deep sequencing of tumor tissue and germ-line, in centers participating in, or with access to the UK framework for this programme.

#### 3.2 Study Treatment (Dosage, Administration and Duration)

The treatment to be used in this trial is outlined below in Table 1, further details can be found in Section 6.

CUPem	C/37/2017	Imperial College London	V7.0; 08.12.2021
-------	-----------	----------------------------	------------------

**Table 1: Trial Treatment**

Drug	Dose/ Potency	Dose Frequency	Route of Administration	Regimen/Treatment Period	Use
Pembrolizumab	200 mg	Q3W	IV infusion	Day 1 of each 3 week cycle	Expe rime ntal

Trial treatment should begin on the day of study entry (screening and consent completed) or as close as possible to the date on which treatment is allocated.

### 3.3 Dose Selection

The rationale for selection of doses to be used in this trial is provided in Section 1.2.2. Details on preparation and administration of pembrolizumab (MK-3475) are provided in the Pharmacy Manual.

#### 3.3.1 Dose Modification (Escalation/Titration/Other)

Adverse events (both non-serious and serious) associated with pembrolizumab exposure may represent an immunologic aetiology. These adverse events may occur shortly after the first dose or several months after the last dose of treatment. Pembrolizumab must be withheld for drug-related toxicities and severe or life-threatening AEs as per Table 2 below. Also see Section 6.9 for supportive care guidelines.

**Table 2: Dose Modification Guidelines for Drug-Related Adverse Events**

Toxicity	Hold Treatment For Grade	Timing for Restarting Treatment	Treatment Discontinuation
Diarrhoea/Colitis	2-3	Toxicity resolves to Grade 0-1	Toxicity does not resolve within 12 weeks of last dose or inability to reduce corticosteroid to 10 mg or less of prednisone or equivalent per day within 12 weeks
	Recurrent 3 or 4	Permanently discontinue	Permanently discontinue
AST, ALT, or Increased Bilirubin	2	Toxicity resolves to Grade 0-1	Toxicity does not resolve within 12 weeks of last dose
	3-4	Permanently discontinue (see exception below) a	Permanently discontinue
Type 1 diabetes mellitus (if new onset) or Hyperglycaemia	T1DM or 3-4	Hold pembrolizumab for new onset Type 1 diabetes mellitus or Grade 3-4 hyperglycaemia associated with evidence of beta cell failure	Resume pembrolizumab when patients are clinically and metabolically stable
Hypophysitis	2-4	Toxicity resolves to Grade 0-1. Therapy with pembrolizumab can be continued while endocrine replacement therapy is instituted	Toxicity does not resolve within 12 weeks of last dose or inability to reduce corticosteroid to 10 mg or less of prednisone or equivalent per day within 12 weeks

CUPem	C/37/2017	Imperial College London	V7.0; 08.12.2021
-------	-----------	----------------------------	------------------

Toxicity	Hold Treatment For Grade	Timing for Restarting Treatment	Treatment Discontinuation
Hyperthyroidism	3	Toxicity resolves to Grade 0-1	Toxicity does not resolve within 12 weeks of last dose or inability to reduce corticosteroid to 10 mg or less of prednisone or equivalent per day within 12 weeks
	4	Permanently discontinue	Permanently discontinue
Hypothyroidism	2-4	Therapy with pembrolizumab can be continued while thyroid replacement therapy is instituted	Therapy with pembrolizumab can be continued while thyroid replacement therapy is instituted
Infusion Reaction	2 b	Toxicity resolves to Grade 0-1	Permanently discontinue if toxicity develops despite adequate premedication
	3-4	Permanently discontinue	Permanently discontinue
Pneumonitis	2	Toxicity resolves to Grade 0-1	Toxicity does not resolve within 12 weeks of last dose or inability to reduce corticosteroid to 10 mg or less of prednisone or equivalent per day within 12 weeks. Treatment will be permanently discontinued if recurrent grade 2 pneumonitis
	3-4	Permanently discontinue	Permanently discontinue
Renal Failure or Nephritis	2	Toxicity resolves to Grade 0-1	Toxicity does not resolve within 12 weeks of last dose or inability to reduce corticosteroid to 10 mg or less of prednisone or equivalent per day within 12 weeks
	3-4	Permanently discontinue	Permanently discontinue
Neurological Toxicities	3-4	Permanently discontinue	Permanently discontinue
Myocarditis	1	Toxicity resolves to Grade 0	Toxicity does not resolve within 12 weeks of last dose or inability to reduce corticosteroid to 10 mg or less of prednisone or equivalent per day within 12 weeks
	2-4	Permanently discontinue	Permanently discontinue
All Other Drug-Related Toxicity c	3 or Severe	Toxicity resolves to Grade 0-1	Toxicity does not resolve within 12 weeks of last dose or inability to reduce corticosteroid to 10 mg or less of prednisone or equivalent per day within 12 weeks
	4	Permanently discontinue	Permanently discontinue

**Note: Permanently discontinue for any severe or Grade 3 drug-related AE that recurs or any life-threatening event.**

a For patients with liver metastasis who begin treatment with Grade 2 AST or ALT, if AST or ALT increases by greater than or equal to 50% relative to baseline and lasts for at least 1 week then patients should be discontinued.

b If symptoms resolve within one hour of stopping drug infusion, the infusion may be restarted at 50% of the original infusion rate (e.g., from 100 mL/hr to 50 mL/hr). Otherwise dosing will be held until symptoms resolve and the subject should be premedicated for the next scheduled dose.

CUPem	C/37/2017	Imperial College London	V7.0; 08.12.2021
-------	-----------	----------------------------	------------------

Toxicity	Hold Treatment For Grade	Timing for Restarting Treatment	Treatment Discontinuation
c Patients with intolerable or persistent Grade 2 drug-related AE may hold study medication at physician discretion. Permanently discontinue study drug for persistent Grade 2 adverse reactions for which treatment with study drug has been held, that do not recover to Grade 0-1 within 12 weeks of the last dose.			

Dosing interruptions are permitted in the case of medical / surgical events or logistical reasons not related to study therapy (e.g., elective surgery, unrelated medical events, patient vacation, and/or holidays). Subjects should be placed back on study therapy within 3 weeks of the scheduled interruption, unless otherwise discussed with the Sponsor. The reason for interruption should be documented in the patient's study record.

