### 4.2 Inclusion Criteria

Patients who meet all of the following inclusion criteria will be considered eligible for this study:

1. Be willing and able to provide written informed consent/assent for the trial.
2. Be  $\geq 18$  years of age on day of signing informed consent.
3. Have measurable disease based on RECIST 1.1.
4. Be willing to provide consent for archival tumour (in the form of formalin fixed paraffin embedded (FFPE) block) or fresh tumour material (if judged technically feasible by radiologist) is mandatory for diagnosis and biomarker analysis.
5. Have a performance status of 0-2 on the ECOG Performance Scale.
6. Have had at least one prior line / regimen of chemotherapy appropriate for CUP (at least 2 cycles). Either did not have a RECIST response to first-line chemotherapy or progressing after an initial response, or are treatment intolerant to first-line chemotherapy due to unacceptable toxicity.
7. Adequate organ and bone marrow function (all screening tests should be performed within 10 days of treatment initiation):
  - a. Absolute neutrophil count (ANC)  $\geq 1.5 \times 10^9/L$
  - b. Platelets  $\geq 100 \times 10^9/L$
  - c. Haemoglobin  $\geq 9$  g/dL ( $\geq 90$  g/L) without transfusion or EPO dependency (within 7 days of assessment)
  - d. Serum creatinine  $\leq 1.5 \times$  Upper Limit of Normal (ULN) or Creatinine clearance\*  $\geq 60$  mL/min for patients with creatinine levels  $> 1.5 \times$  ULN  
\* Creatinine clearance should be calculated per institutional standard
  - e. Serum total bilirubin  $\leq 1.5 \times$  ULN or direct bilirubin  $\leq$  ULN for patients with total bilirubin levels  $> 1.5$  ULN
  - f. Aspartate aminotransferase [AST]  $\leq 2.5 \times$  ULN ( $< 5 \times$  ULN if liver metastases are present)
  - g. Alanine aminotransferase [ALT]  $\leq 2.5 \times$  ULN ( $< 5 \times$  ULN if liver metastases are present)
  - h. Albumin  $\geq 2.5$ g/dL
  - i. International Normalized Ratio (INR) or Prothrombin Time (PT)  $\leq 1.5 \times$  ULN (unless subject is receiving anticoagulant therapy as long as PT or PTT is within therapeutic range of intended use of anticoagulants)
  - j. Activated Partial Thromboplastin Time (APTT)  $\leq 1.5 \times$  ULN (unless subject is receiving anticoagulant therapy as long as PT or PTT is within therapeutic range of intended use of anticoagulants).

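### Table 2 footnote a is tied only to the Grade 3-4 liver line and is not reconciled with the Grade 2 line for patients with liver metastases who enter at Grade 2 AST/ALT

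*Protocol*

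**What the plan says.** Protocol Section 4.2, items 7f and 7g (repeated in SAP Section 3.4), caps AST and ALT at 2.5 x ULN but relaxes this to below 5 x "ULN if liver metastases are present".

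Table 2 is headed "Dose Modification Guidelines for Drug-Related Adverse Events", and Section 3.3.1 introduces it with: "Pembrolizumab must be withheld for drug-related toxicities and severe or life-threatening AEs as per Table 2 below". Its row for AST, ALT or bilirubin has two lines:

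- **Grade 2.** Hold. The restart cell reads "Toxicity resolves to Grade 0-1" and the discontinuation cell reads "Toxicity does not resolve within 12 weeks of last dose". There is no footnote marker and no mention of baseline.
- **Grade 3-4.** Listed in the column of grades for which treatment is held. The restart cell reads "Permanently discontinue (see exception below"), and this is the only place where marker a appears.

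Footnote a names its population as follows: "For patients with liver metastasis who begin treatment with Grade 2 AST or ALT". For them it requires treatment to stop once either enzyme has risen by 50% or more over its baseline value and has stayed there for a week or longer. It gives no instruction for smaller or shorter rises.

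The hepatic part of Section 6.8.1 has liver tests monitored more often after a Grade 2 event until they are back at baseline.

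**The concern.** The protocol admits a group that starts at Grade 2 and writes a baseline-relative footnote for it, but attaches that footnote to the Grade 3-4 line alone. If such a patient has a drug-related rise within Grade 2, the site is left with an absolute restart level that lies below the value at which the patient was enrolled. Where the rise is also large and sustained, the Grade 2 line and the footnote set different points for stopping.

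Two sites could therefore handle the same laboratory series differently: one waits up to 12 weeks for resolution and the other stops after a week. That matters for consistent safety management. It also matters for exposure and for the counts of permanent discontinuation by reason, which Section 6.9.6 requires to be recorded.

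**Working it through.** The plan states no figure to reproduce. The check sets the passages side by side and adds simple arithmetic.

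**Inputs from the protocol.** Entry below 5 x ULN with liver metastases (4.2, 7f/7g). Restart at Grade 0-1 and a 12-week limit (Table 2, Grade 2 liver line). A rise of at least 50% over baseline for at least 1 week (footnote a).

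**Assumptions.** Section 7.2.1 cites CTCAE 4.03 but the documents do not print its AST/ALT limits. Grade 2 is taken to end at 5 x ULN and to begin above L, with L varied from 2.5 to 3.0 x ULN.

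**Formulas**, with b the entry value in multiples of ULN:

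- Footnote trigger: T = 1.5 x b.
- Fall below entry needed to reach Grade 1: D = 1 - L/b.
- The trigger lies within Grade 2 when 1.5 x b is at most 5, so b is at most 5/1.5 = 3.33.

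**1. Drug-related rise of under 50%, still Grade 2.** Take b = 4.0 rising to 4.8: 4.8/4.0 = 1.20, or +20%. T = 6.0 is not reached, so only the Grade 2 line gives an instruction, which is to hold. For restart, D = 1 - 3.0/4.0 = 25%, or 1 - 2.5/4.0 = 37.5%. For b = 4.99, D is 39.9% to 49.9%. For b just above L it is close to zero. Return to the entry value does not satisfy the restart cell, and at 12 weeks the line discontinues.

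**2. Drug-related rise of at least 50% for at least a week, still Grade 2.** This needs b up to about 3.33. Take b = 3.1 rising to 4.7: 4.7/3.1 = 1.52, or +52%, above T = 4.65. The line allows up to 12 weeks to resolve; the footnote, read by its own wording, discontinues after 1 week. The entry range concerned is 3.0 to 3.33 (0.33 of a width of 2.0, about 17%) or 2.5 to 3.33 (0.83 of 2.5, about 33%). These are shares of the laboratory range, not of patients.

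**3. Drug-related rise into Grade 3 of under 50%.** This needs b above 3.33. Take b = 4.9 rising to 6.0: 6.0/4.9 = 1.22, or +22%, below T = 7.35. The flagged exception lifts permanent discontinuation. The hold remains, because Grade 3-4 stands in the hold column, but no restart level replaces the cell that the exception displaces.

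**4. Cases 1 and 3 together.** Followed literally, a patient who rose from 4.0 to 4.8 and settled back at 4.0 is discontinued at 12 weeks. A patient who rose from 4.9 to 6.0 is exempt from the permanent stop.

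**5. Baseline wording elsewhere.** Section 6.8.1 follows Grade 2 hepatic events to baseline, and the recovery conditions in exclusion criteria 5 and 6 accept either Grade 1 or the baseline level. The Grade 2 liver line has no such alternative. Neither of those sections sets a restart level.

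**The case against.** A reader might infer that the row and the footnote order opposite actions for the whole subgroup, or that one result could lead a site to continue dosing, to hold or to stop. The text does not go that far. Nothing tells a site to continue: the footnote only sets a point for stopping, and not reaching it is not permission to dose. In case 1 there is one instruction, the hold. At Grade 3-4 the footnote is an announced exception, not a contradiction, and a hold is stated, so only a restart level is missing. The note under Table 2 also covers a Grade 3 drug-related event that recurs.

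A reader might also infer that a patient enrolled at Grade 2 cannot be dosed at all. Table 2 covers drug-related events, so an unchanged entry value triggers nothing. Nor do the documents show that these are the patients with least hepatic reserve; entry also requires limits on bilirubin, albumin and clotting.

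Case 2 can be read as a sequence: hold first, then stop if the large rise lasts a week. It can also be read as no conflict at all, if the marker confines the footnote to Grade 3-4. Either reading is reasonable, but they lead to different stopping points, and the protocol does not say which applies. Case 2 is also confined to low Grade 2 entry values.

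These points narrow the concern considerably. They do not remove the restart level below the entry value in case 1, the unsettled stopping point in case 2 or the missing restart level in case 3.

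**Conclusion.** The inconsistency is real and limited. For patients with liver metastases who enter at Grade 2 AST/ALT and then have a drug-related rise:

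- within Grade 2, restart requires a value below entry: by 25% to 37.5% for an entry value of 4.0 x ULN, and by about 40% to 50% for one just under 5;
- for a rise of at least 50% lasting at least a week within Grade 2, the line and the footnote differ on when to discontinue (12 weeks against 1 week), for entry values up to about 3.33 x ULN;
- for a rise into Grade 3 of under 50%, a hold applies but no restart level is stated.

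The figures rest on assumed Grade 2 limits of 2.5-3.0 to 5 x ULN. The mismatch in wording does not depend on the exact limits. The number of patients affected cannot be estimated from the documents. The point is worth correcting, but it does not bear on the trial's sample size or primary analysis method.

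**What to change.** Reconcile the Grade 2 liver line, the Grade 3-4 liver line, footnote a and the hepatic guidance in Section 6.8.1 for patients who enter at Grade 2 AST/ALT. State which provision governs them for hold, restart and discontinuation, and whether footnote a applies outside Grade 3-4. The clinical rule and its thresholds are for the investigators and sponsor to decide; this review takes no view on them.

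The cost is a wording change to one table row and its footnote in a protocol amendment. No new tests are needed, since AST and ALT are already measured before each dose (Table 3 and Section 5.9.12).

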### 3.4 Timing of Dose Administration

Trial treatment should be administered on Day 1 of each cycle after all procedures/assessments have been completed as detailed in the Table of Assessments (Section 5.0). Trial treatment may be administered up to 3 days before or after the scheduled Day 1 of each cycle due to administrative reasons.

All trial treatments will be administered on an outpatient basis. Pembrolizumab 200 mg will be administered as a 30 minute IV infusion every 3 weeks. Sites should make every effort to target infusion timing to be as close to 30 minutes as possible. However, given the variability of infusion pumps from site to site, a window of -5 minutes and +10 minutes is permitted (i.e., infusion time is 30 minutes: -5 min/+10 min).

[figure not shown]
The Pharmacy Manual contains specific instructions for the preparation of the pembrolizumab infusion fluid and administration of infusion solution. This is an open-label trial; therefore, the Sponsor, investigator and subject will know the treatment administered from the outset.

Treatment will continue until unacceptable treatment-related toxicity, disease progression or patient and/or Investigator decision.

CUPem	C/37/2017	Imperial College London	V7.0; 08.12.2021
-------	-----------	----------------------------	------------------

### 3.5 Study Flow Chart

**Figure 2: Study Flow Chart**

CUPem	C/37/2017	Imperial College London	V7.0; 08.12.2021
-------	-----------	----------------------------	------------------

## 4 PARTICIPANT ENTRY

### 4.1 Study setting and population

This trial will be performed at three investigational sites in England, and recruit patients with cancer of an unknown primary. See full Eligibility Criteria below.

### 4.2 Inclusion Criteria

Patients who meet all of the following inclusion criteria will be considered eligible for this study:

1. Be willing and able to provide written informed consent/assent for the trial.
2. Be  $\geq 18$  years of age on day of signing informed consent.
3. Have measurable disease based on RECIST 1.1.
4. Be willing to provide consent for archival tumour (in the form of formalin fixed paraffin embedded (FFPE) block) or fresh tumour material (if judged technically feasible by radiologist) is mandatory for diagnosis and biomarker analysis.
5. Have a performance status of 0-2 on the ECOG Performance Scale.
6. Have had at least one prior line / regimen of chemotherapy appropriate for CUP (at least 2 cycles). Either did not have a RECIST response to first-line chemotherapy or progressing after an initial response, or are treatment intolerant to first-line chemotherapy due to unacceptable toxicity.
7. Adequate organ and bone marrow function (all screening tests should be performed within 10 days of treatment initiation):
  - a. Absolute neutrophil count (ANC)  $\geq 1.5 \times 10^9/L$
  - b. Platelets  $\geq 100 \times 10^9/L$
  - c. Haemoglobin  $\geq 9$  g/dL ( $\geq 90$  g/L) without transfusion or EPO dependency (within 7 days of assessment)
  - d. Serum creatinine  $\leq 1.5 \times$  Upper Limit of Normal (ULN) or Creatinine clearance\*  $\geq 60$  mL/min for patients with creatinine levels  $> 1.5 \times$  ULN  
\* Creatinine clearance should be calculated per institutional standard
  - e. Serum total bilirubin  $\leq 1.5 \times$  ULN or direct bilirubin  $\leq$  ULN for patients with total bilirubin levels  $> 1.5$  ULN
  - f. Aspartate aminotransferase [AST]  $\leq 2.5 \times$  ULN ( $< 5 \times$  ULN if liver metastases are present)
  - g. Alanine aminotransferase [ALT]  $\leq 2.5 \times$  ULN ( $< 5 \times$  ULN if liver metastases are present)
  - h. Albumin  $\geq 2.5$ g/dL
  - i. International Normalized Ratio (INR) or Prothrombin Time (PT)  $\leq 1.5 \times$  ULN (unless subject is receiving anticoagulant therapy as long as PT or PTT is within therapeutic range of intended use of anticoagulants)
  - j. Activated Partial Thromboplastin Time (APTT)  $\leq 1.5 \times$  ULN (unless subject is receiving anticoagulant therapy as long as PT or PTT is within therapeutic range of intended use of anticoagulants).
8. Female subject of childbearing potential should have a mandatory negative serum pregnancy within 72 hours prior to receiving the first dose of study medication.
9. Female subjects of childbearing potential must be willing to use an adequate method of contraception as outlined in Section 6.9.2 – Contraception, for the course of the study through 120 days after the last dose of study medication.

CUPem	C/37/2017	Imperial College London	V7.0; 08.12.2021
-------	-----------	----------------------------	------------------

Note: Abstinence is acceptable if this is the usual lifestyle and preferred contraception for the subject.

- Male subjects of childbearing potential must agree to use an adequate method of contraception as outlined in Section 6.9.2 - Contraception, starting with the first dose of study therapy through 120 days after the last dose of study therapy.

Note: Abstinence is acceptable if this is the usual lifestyle and preferred contraception for the subject.

